5.3.2. Criteria for permanent discontinuation of the IMP

The IMP must be discontinued in the case:

- Upon initiation of renal replacement therapy;
- Upon increase of ALT and/or AST to ≥ 3 x ULN and total bilirubin > 2 x ULN or upon increase of ALT and/or AST to ≥ 5 x ULN
- The patient is discharged home;
- Withdrawal of informed consent by the patient or his/her legal representative (in this case, the patient / representative will be asked whether they consent to usage of the data already collected in the study; if not, the data will be deleted);
- Pregnancy occurs;
- Development of Serious AE probably or possibly related to IMP, as per PI's judgment;
- Inadvertent missing of 3 or more consecutive doses of the IMP;
- Inability to resolve within 24 hours any medical condition/event that led to temporary withholding of the IMP (see also 5.3.3.);
- Recurrence of AE probably or possibly related to IMP upon re-introduction of the IMP.

Occurrence of renal or hepatic dysfunction will be monitored as part of the biochemistry data set through safety laboratory tests obtained at day 3 ± 8 h, 7 ± 1 , 14 ± 2 , and 21 (if the IMP is meant to be administered up to 21 days). The other criteria that qualify the patient to treatment discontinuation will be monitored daily.

If the IMP administration is prematurely discontinued, the primary reason for discontinuation must be recorded in the eCRF. Patients who discontinue the treatment with the IMP will NOT be withdrawn from the study by default and will be asked to complete safety and efficacy observations as per the protocol unless they withdraw their consent.

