3.1 General design and plan

This is an international, multicenter, 1:1 randomized, double-blind, placebo-controlled, phase II proof-of-concept trial. It will enroll approximately 66 adult patients hospitalized with ARDS that meet the inclusion criteria, randomly assigned at 1:1 ratio to receive either reparixin 1200 mg (treatment group) through a nasogastric tube or matched placebo (control group) TID for 14 days with optional continuation of treatment up to 21 days, if patient is still intubated on Day 14.

All patients must receive standard and supportive care according to their clinical status and local guidelines during the whole study period.

Each patient will be involved in the study for up to 60 days.

The study will consist of 4 study periods:

- Screening
- Randomization and Baseline assessments
- Treatment (14 days, with the option of extension up to 21 days if the patient is still intubated on Day 14)
- Follow-up (up to 28 days and hospital discharge if later than 28 days; and then up to day- 60).

Patients will be assessed daily while hospitalized up to extubation from first IMP administration. The end of this study is defined as the end of follow-up.

If the patient discontinues treatment prematurely without withdrawing his consent and without being discharged from the hospital, subsequent visits will be done according to study Protocol.

Standard/Forms/Template				
Title		Statistical Analysis Plan Template		
Code		Version	Effective Date	Page
PPD		01	29 Aug 2022	14 of 78

If the patient discontinues treatment prematurely without withdrawing his consent but was discharged from the hospital, he will have to complete the hospital discharge visit and the follow-up visit at Day 60.

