18. CCI

Standard/Forms/Template				
Title		Statistical Analysis Plan Template		
Code		Version	Effective Date	Page
PPD		01	29 Aug 2022	19 of 78

19. If hospital discharge occurs <28d, a 28-d follow-up in-person visit should be performed. If this is not feasible, a phone follow-up will be planned to collect: Duration of IMV, ICU length of stay, need for reintubation, Hospital length of stay, performance of tracheostomy, transfer to LTAC* facility, or mortality.

CCI

21. Only at hospital discharge

*An LTAC is a Long Term Acute Care Hospital, i.e., a facility that specializes in the treatment of patients with serious medical conditions, including patients with ongoing needs for mechanical ventilation, but who no longer require intensive care or extensive diagnostic procedures. The patients in LTAC are transferred there directly from the intensive care unit because they require more care than they can receive in a rehabilitation center, skilled care facility or at home.

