Retrieved drop-out flag for ventilatory free days at day 28	
For "VFD at Day 28" the retrieved dropouts are the patients that discontinued the study treatment (treatment completers/discontinuers are defined above in this table under "Treatment completed/discontinued") and have the endpoint evaluable by Day 28 (death on the day of the treatment discontinuation not part of the retrieved dropout):
 
Set to 'Y' if Subject discontinued the treatment prematurely and patient is alive or have date of death after end of treatment, and the endpoint is not missing for this parameter and timepoint.

Standard/Forms/Template				
Title		Statistical Analysis Plan Template		
Code		Version	Effective Date	Page
PPD		01	29 Aug 2022	63 of 78

Parameter	Calculation
Change in oxygenation index (OI) from baseline to day 4 [study day based on Date/time]	
The endpoint is derived similarly to change from baseline at day 7.
 
 - If patient dies before Day 4, or at Day 4 (Day 4 date = Day 1 date + 3, since only date of death -no time- is collected) and OI is missing: OI at day 4 = 90th percentile of the distribution of the primary variable at Day 4. - If patient at Day 4 is extubated* and OI is not evaluable (i.e., if the patient results not intubated* in the time range [First IMP Intake Date/Time +60h, First IMP Intake Date/Time +83h and 59 min]), OI at day 4 = 10th percentile of the distribution of the primary variable at Day 4. - Otherwise, OI is set to missing. 
*intubation/extubation status at day 4: check intubations in "Extubation Summary" CRF form. Use the multiple entries of extubation/re-intubation: if the last record of intubations/extubations prior day 4 is an extubation, and there are no intubations at day 4, it means the subject was extubated on Day 4.

ICU stay up to Day 28 and up to hospital discharge (days)	The information on ICU length of stay is collected under "Other Clinical Event Form" at Day 28 Visit and at Hospital Discharge Visit

Standard/Forms/Template				
Title		Statistical Analysis Plan Template		
Code		Version	Effective Date	Page
PPD		01	29 Aug 2022	64 of 78

Parameter	Calculation

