ICU-free days at Day 28 and at hospital discharge (days) [study day based on Date]	
ICU-free days at Day 28
 
If patient is alive at Day 28 (last available day \geq 26) and ICU-free days is not missing at Day 28: ICU-free days = 28 – ICU stay up to Day 28.[^]
 
Else, If patient is discharged before Day 28 (date of discharge is not missing and date of discharge $<$ Day 28) and the patient died after hospital discharge and before day 28 (hospital discharge $<$ date of death $<$ Day 28) then ICU-free days at day 28= ICU-free days at discharge
 
If patient dies within Day 28 : ICU-free days = 0
 
If subject is alive and followed for $<$ 26 days (last available date $<$ 26) the endpoint is set as missing.
 
Otherwise, the endpoint will be set as missing.
 
[^]in case of negative values, it is assumed that ICU-free days = 0.
 
Day 28= Day 1 date + 27
 
ICU-free days at Hospital Discharge
 
If patient is alive at hospital discharge date* (last available date $>$ hospital discharge date*): ICU-free days = [hospital discharge date* – First IMP Intake date + 1] – ICU stay up to hospital discharge date*. [^]
 
If patient is never discharged (date of discharge is missing) and the patient died after day 28 (date of death $>$ Day 28), then ICU-free days at discharge=ICU-free days at day 28
 
Else (If patient dies within hospital discharge date*) or (if date of death is not missing and it is prior to Day 28 (date of death $<$ Day 28) and discharge date is missing (i.e., subjects died during hospitalization)): ICU-free days = 0
 
Otherwise, the endpoint is set as missing.
 
[^]in case of negative values, it is assumed that ICU-free days = 0.
 
*date of discharge is collected in End of Study form; in the case it is missing it is taken from Visit date in "Hospital Discharge".

Standard/Forms/Template				
Title		Statistical Analysis Plan Template		
Code		Version	Effective Date	Page
PPD		01	29 Aug 2022	65 of 78

Parameter	Calculation

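### ICU-free days at Day 28 is set to missing for a patient discharged alive before Day 28 who has no Day 28 ICU entry, although the discharge form holds the ICU stay

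*SAP*

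**What the plan says.** **Derivation.** In SAP 11.1.1, Table 3, a patient alive at Day 28 gets 28 minus the ICU stay, on the condition "If patient is alive at Day 28 (last available day \geq 26) and ICU-free days is not missing at Day 28". A second line borrows ICU-free days at discharge, but only if "the patient died after hospital discharge and before day 28". A third reads "If patient dies within Day 28 : ICU-free days = 0". Anyone left over is set to missing.

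**Source of the ICU stay.** Table 3 says it is collected "at Day 28 Visit and at Hospital Discharge Visit".

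**Follow-up after early discharge.** Note 19 to the schedule, in both the protocol (section 2) and SAP Table 1, says "If hospital discharge occurs <28d, a 28-d follow-up in-person visit should be performed". If a visit is not feasible, a phone call is to collect a list of items that includes ICU length of stay. SAP 3.1 reads differently for a patient who stops treatment prematurely, keeps consent and has been discharged: "he will have to complete the hospital discharge visit and the follow-up visit at Day 60". It names no Day 28 contact.

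**Missing data.** SAP 4.10 reserves multiple imputation for the primary endpoints and summarises continuous data on non-missing values. SAP 7.2.1.9 compares ICU-free days by t-test, adding a Mann-Whitney test if normality fails.

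**The concern.** A patient who has left hospital alive is, barring readmission, out of the ICU, and the ICU stay is already recorded at discharge. The rule discards that information when the Day 28 entry is absent, although it borrows discharge data for a patient who went home and then died. Those lost are survivors who left hospital before Day 28, which is a good outcome. Patients who die in hospital need no Day 28 entry and stay in at 0. Missingness is then tied to outcome. If reparixin works partly by bringing discharge forward, more good outcomes are exposed to loss in that arm and the estimated benefit shrinks.

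**Working it through.** The documents state no figure for ICU-free days, so there is none to reproduce. The check applies the rule to test patients and then sizes the effect under stated assumptions.

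**1. Test patients.** Hospital stay and ICU-free days at discharge follow Table 3: discharge date minus first-dose date plus 1, which is 12 for discharge on Day 12.

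| Patient | Result under Table 3 |
|---|---|
| A. Discharged Day 12, 8 ICU days, alive at Day 60, no Day 28 form | missing |
| B. As A, but Day 28 phone data obtained | 28 - 8 = 20 |
| C. Discharged Day 12, 8 ICU days, died Day 20 | 12 - 8 = 4 on one line, 0 on the next |
| D. Died in hospital on Day 10 | 0 |
| E. Discharged Day 26, 15 ICU days, alive, no Day 28 form | missing; 28 - 15 = 13 if re-mapping applies |

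Patient A has 28 - 12 = 16 hospital-free days. That endpoint and ventilator-free days rely on last available day of at least 26, which follow-up to Day 60 meets, and need no Day 28 ICU entry.

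**2. Can re-mapping rescue patient A?** No. SAP 3.2.3 applies to endpoints that use nominal visits, and SAP 3.5.2 labels ICU-free days as date-based. Even if it applied, the discharge must fall inside the Day 28 ±2 window, which helps patient E but not patient A.

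**3. Size.** Assumptions: deaths score 0; early discharges average 18 ICU-free days; other survivors average 8. Mortality is 36% in both arms, the midpoint of the 27% to 45% range in protocol 2.6.2.3 (not stated there as 28-day mortality). Early discharge is 30% on reparixin and 20% on placebo. With m the mortality, e the early-discharge share and q the share of early discharges lacking Day 28 data:

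observed mean = [18e(1 - q) + 8(1 - m - e)] / (1 - eq)

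| q | Reparixin | Placebo | Difference |
|---|---|---|---|
| 0 | 5.40 + 2.72 = 8.12 | 3.60 + 3.52 = 7.12 | +1.00 |
| 25% | 6.77/0.925 = 7.32 | 6.22/0.95 = 6.55 | +0.77 |
| 50% | 5.42/0.85 = 6.38 | 5.32/0.90 = 5.91 | +0.47 |
| 75% | 4.07/0.775 = 5.25 | 4.42/0.85 = 5.20 | +0.05 |
| 100% | 2.72/0.70 = 3.89 | 3.52/0.80 = 4.40 | -0.51 |

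Varying mortality over 27% to 45% and early discharge over 10% to 30%, a single arm's mean falls by 0.3 to 0.9 days at q = 25%, 0.6 to 1.9 at 50% and 1.2 to 4.5 at 100%.

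**4. Patients involved.** With 66/2 = 33 per arm, early discharge of 20% to 30% is 6.6 to 9.9 patients. At q = 25%, that is about 1.7 to 2.5 patients lost per arm.

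**The case against.** The strongest reply is that Day 28 data are planned for everyone concerned. Note 19 covers every discharge before Day 28, its phone fallback collects ICU length of stay, and protocol 5.3.2 and 6.2.1 ask patients who stop the study drug to continue observations. That stands: the loss needs a failed contact or a site working to SAP 3.1, and with full contact the bias is zero.

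A reader might infer that SAP 3.1 systematically routes the fastest recoveries past Day 28, because protocol 5.3.2 lists "The patient is discharged home" among the mandatory reasons to stop the study drug. The documents do not support this. SAP 3.1 covers premature discontinuers only, while Table 3 counts discharge home as treatment completion. Patients who finish treatment and leave before Day 28 are also outside SAP 3.1. At most, its reach is unclear.

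A reader might also infer that the treatment difference would reverse. In the illustration the sign changes only when more than 75% of early discharges lack data. Under other assumptions (35% mortality in both arms, early discharge 20% vs 10%, means of 21 and about 8.4 days), +1.26 becomes +0.94 at 25% missing and +0.57 at 50%, and turns negative only above about 80%. With note 19 in place, nothing suggests loss on that scale.

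Nor does every death score 0: Table 3 gives a death after discharge and before Day 28 the discharge value on one line and 0 on the next.

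Finally, ICU-free days at hospital discharge uses the discharge form and keeps these patients, though on a different scale. None of this supplies the missing fallback for a survivor.

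**Conclusion.** The gap in the derivation is real. As written, Table 3 discards a known good outcome when the Day 28 ICU entry is absent, and no other rule reliably recovers it. The direction is dilution of any benefit that acts through earlier discharge. The size depends on how many early discharges lack Day 28 data, which the documents do not give and which may be none. Under the assumptions shown, a true +1.0 day falls to +0.77 with a quarter missing and +0.47 with half missing. These figures rest on assumed early-discharge rates and ICU-free-day means with no source in the documents, and on missingness being equally likely in both arms.

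The consequence is limited to one descriptive secondary endpoint. Neither primary endpoint uses the Day 28 ICU entry.

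**What to change.** 1. Add to Table 3: for a patient discharged alive before Day 28, alive at Day 28 (last available day at least 26) and with the Day 28 ICU stay missing, ICU-free days = 28 minus the ICU stay from the Hospital Discharge form, assuming no ICU readmission.
2. Make the survivor line depend on the ICU stay being present. It now tests whether the endpoint itself is present, which is circular.
3. Reconcile the two lines that give a death after discharge and before Day 28 either the discharge value or 0.
4. Align SAP 3.1 with note 19 for consistency. SAP version 2.0 is dated 30 July 2025 and the protocol planned the last visit for February 2025. On those dates this change would probably recover no data, so item 1 does the work.

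Count the affected patients at the blinded data review (SAP 4.12) and report the number. If it is zero, item 1 changes nothing.

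The cost is one line of derivation code and a few sentences. The small downside is that an ICU readmission after discharge would be missed where no Day 28 contact took place.

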7. STUDY ENDPOINTS

7.1. EFFICACY ENDPOINTS

Primary endpoint:

- Change in oxygenation index (**OI**) from baseline to day 7 of treatment. The OI is defined as: % mean airway pressure x $\text{FIO}_2/\text{PaO}_2$
- Ventilator free days (**VFD**) at day 28 (see 14.4.11)

[figure not shown]
Secondary endpoints:

- Change in OI from baseline to day 4
- Acute lung injury score [composite of $\text{PaO}_2/\text{FIO}_2$ ratio, PEEP, lung compliance (plateau airway pressure minus PEEP/TV) and extent of pulmonary infiltrates] at 2, 3, 7, 14 days (if still intubated)
- SOFA scores at 2, 3, 7, 14 days (if still intubated)
- Ventilatory ratio (product of minute ventilation and PaCO_2) at 2, 3, 7, 14 days (if still intubated)
- Incidence of ECMO at day 14
- Use of vasoactive medications at day 14
- CXR assessment of pulmonary edema by “radiographic assessment of lung edema” (**RALE**) score at 2, 3, 7, 14 days
- Percentage of patients achieving pressure support ventilation equal to 5 cm H₂O with PEEP equal to 5 cm H₂O for 2 hours (measure of weaning) by day 28 and hospital discharge
- ICU-free days by day 28 and hospital discharge
- Hospital-free days by day 28 and hospital discharge
- Incidence of tracheostomies by day 28 and hospital discharge
- Incidence of LTAC facility by day 28 and hospital discharge
- All-cause mortality by day 28
- Hospital discharge by day 28
- All-cause mortality by day 60
- Change from baseline to day 3, 7 and 14 in plasma levels of IL-6, IL-8, PAI-1, Plasma TNFr-1, ICAM-1 RAGE

Footnote: day 1 is the day when the IMP is first administered. Hour 1 of day 1 starts when the first dose of the IMP is administered. Subsequent days are measured in 24-hour intervals from hour 1. Therefore, day 2(± 8 h) signifies 24 hours ± 8 hours from hour 1.

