4.11 Changes in the planned analysis

The following changes have been included compared to the study protocol:

- Section 4.2.3: The Primary Analysis (including sensitivity analysis) is planned on the Randomized Set, as per Regulatory Authority request. Full Analysis set will be used for Supplementary Analysis and for analysis of secondary endpoints.
- Protocol section 9.5 mentions "Subjects who are free from events at the time of DB lock will be censored at the DB lock date. Reasons for discontinuation will be incorporated into the analysis for determining censoring and failure status. Specifically, study discontinuation for Adverse Event, Death, Lost to follow-up or other negative outcomes will be considered as failure events." As per SAP, other negative outcomes will not be considered in the analysis: only study discontinuation for Adverse Event, Death or Loss to follow-up will be considered as

Standard/Forms/Template				
Title		Statistical Analysis Plan Template		
Code		Version	Effective Date	Page
PPD		01	29 Aug 2022	33 of 78

failure events. Also, it has been added in the SAP that subjects free of events are censored at last available date.

- Protocol section 9.5.1.1 mentions “Normal distribution will be assessed graphically.”: for the two co-primary endpoints normality assumptions will be checked through visual inspection and statistical tests (Shapiro-Wilk’s test) as detailed in section 4.1, while for all other relevant endpoints normality is checked only via statistical test (Shapiro-Wilk’s test).
- **CCI**
[REDACTED]
- **CCI**
[REDACTED]
- Sensitivity and supplementary analysis have been added as described in SAP sections 7.1.2 and 0
- A new analysis has been added to be performed only on the subset of complete cases (i.e., without considering patients with missing endpoint) that reached Day 7 still intubated: details are provided in SAP section 7.1.3.6.
- The study protocol mentions among the secondary endpoints “Hospital-free days by day 28 and hospital discharge”: the endpoint will be evaluated only at day 28 (“Hospital-free days by day 28”) since at discharge the number of hospital-free days will be 0 by definition.

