7.2.1.9 ICU-free days at Day 28 and at Hospital Discharge

Rules for derivation of ICU-free days are reported in section 11.1.

ICU-free days will be analyzed by means of descriptive statistics as a continuous variable at Day 28 and at hospital discharge. Comparison between treatments will be performed by means of two-sample t-test and, if assumptions of normality is not confirmed, two-sample Mann-Whitney U test.

Standard/Forms/Template				
Title		Statistical Analysis Plan Template		
Code		Version	Effective Date	Page
PPD		01	29 Aug 2022	50 of 78

7.2.1.10 Hospital-free days at Day 28

Rules for derivation of hospital-free days are reported in section 11.1.

The hospital-free days by Day 28 will be analyzed by means of descriptive statistics as a continuous variable. Comparison between treatments will be performed by means of two-sample t-test and, if assumptions of normality is not confirmed, two-sample Mann-Whitney U test.

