Hospital stay up to Day 28 (days) [study day based on Date]	
Hospital stay up to Day 28 :
 
Date of discharge* – First IMP Intake date + 1.
 
If Date of discharge* is after Day 28 date, then Day 28 date will be used instead.
 
If Date of discharge* is missing and date of death\geq Day 28 date then date of Discharge = Day 28 date.
 
If Date of discharge* is missing and last available day \geq 26 then date of Discharge = Day 28 date.
 
Otherwise the endpoint is set as missing.
 
Day 28 date: Day 1 date + 27
 
*date of discharge is collected in End of Study form; in the case it is missing it is taken from Visit date in "Hospital Discharge".

Hospital-free days by Day 28 [study day based on Date]	
Hospital-free days by Day 28
 
If patient is alive at Day 28 (last available day \geq 26): Hospital-free days = 28 – Hospital stay up to Day 28
 
If patient dies within Day 28: Hospital-free days = 0
 
Otherwise, If subject is alive and followed for $<$ 26 days (last available day $<$ 26) the endpoint is set as missing.
 
Day 28= Day 1 date + 27

Standard/Forms/Template				
Title		Statistical Analysis Plan Template		
Code		Version	Effective Date	Page
PPD		01	29 Aug 2022	66 of 78

Parameter	Calculation
Patients discharged (alive) by Day 28 [study day based on Date]	
A patient is considered discharged alive by Day 28:
 
 - if patient is discharged* before Day 28 (included) (regardless the vital status after discharge). 
Otherwise, a patient is considered not alive and discharged by Day 28:
 
 - if patient dies and date of discharge* is missing, OR - if patient is not discharged* before Day 28 (included) (day of discharge >28) OR - if date of discharge is missing, but subject is in study long enough (last available day ≥ 26) OR - Discharge date=Death date (assumptions: patient died in the hospital) 
Otherwise, if the date of discharge is missing and subject is alive and followed for <26 days (last available date<26) the endpoint is set as missing.
 
Day 28: Day 1 + 27
 
*date of discharge is collected in EOS; in the case it is missing it is taken from Visit date in "Hospital Discharge".

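### ICU-free days at hospital discharge has no fixed horizon, so for a given ICU stay an earlier discharge scores worse; the death rules for ICU-free days also need repair

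*SAP*

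**What the plan says.** Protocol 7.1 lists "ICU-free days by day 28 and hospital discharge" among the secondary endpoints. SAP 7.2.1.9 keeps both time points: "ICU-free days will be analyzed by means of descriptive statistics as a continuous variable at Day 28 and at hospital discharge". It compares the arms by t-test, adding a Mann-Whitney test if normality is not confirmed.

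SAP 11.1.1, Table 3, gives the derivations.

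- **Day 28 version, alive at Day 28:** 28 minus ICU stay, with negative values set to 0.
- **Day 28 version, deaths:** a patient discharged before Day 28 who then dies before Day 28 takes the discharge score. The next line, which opens with a plain 'If', gives 0 to any death within Day 28.
- **Discharge version, alive at discharge:** "ICU-free days = [hospital discharge date* – First IMP Intake date + 1] – ICU stay up to hospital discharge date", with negative values set to 0.
- **Discharge version, deaths:** "If patient is never discharged (date of discharge is missing) and the patient died after day 28", "then ICU-free days at discharge=ICU-free days at day 28". The score is 0 if death falls on or before a recorded discharge date, or if death precedes Day 28 and the "discharge date is missing (i.e., subjects died during hospitalization"). All remaining cases are missing.

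In the same table, ventilator-free days and hospital-free days are 0 for every death by Day 28, with no exception for death after discharge.

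**The concern.** A free-days score is meant to rise as patients recover faster. That needs a window of the same length for everyone. In the discharge version the window is the patient's own hospital stay, so the score counts inpatient days outside the ICU. More of those days can mean a shorter ICU stay or a slower discharge, and the score cannot tell them apart. The trial's stated objective includes faster clinical recovery, so a treatment that brings discharge forward could look neutral or harmful here.

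The death rules matter for a different reason. Free-days scores usually give death the worst value. Here the value given to a death depends on which side of Day 28 it falls, on whether a discharge date was entered, and on how the programmer orders the lines. An in-hospital death can then rank above a quick recovery.

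**Working it through.** The plan states no figure for this endpoint, so the check applies the Table 3 rules to example patients. The ICU stays and dates are illustrative assumptions. Day 1 is the day of first dose, and ICU stay is first taken as counted from that day.

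Let D be the study day of discharge (discharge date minus first-dose date plus 1) and I the ICU days.

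- Discharge version, alive at discharge: max(0, D − I)
- Day 28 version, alive at Day 28: max(0, 28 − I)

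**Step 1: same ICU stay, different discharge day.** With I = 8, D = 10 gives 10 − 8 = 2 and D = 20 gives 20 − 8 = 12. The Day 28 version gives 28 − 8 = 20 for both. A patient who goes home straight from the ICU (I = 10, D = 10) scores 0, the value the rules otherwise use for death; the Day 28 version gives 18.

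**Step 2: a treatment that shortens ICU stay by 4 days.**

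| Course | I | D | Discharge version | Change | Day 28 version | Change |
|---|---|---|---|---|---|---|
| Reference | 14 | 24 | 24 − 14 = 10 | | 28 − 14 = 14 | |
| Ward stay unchanged | 10 | 20 | 20 − 10 = 10 | 0 | 28 − 10 = 18 | +4 |
| Ward stay 4 days shorter | 10 | 16 | 16 − 10 = 6 | −4 | 18 | +4 |
| Ward stay 4 days longer | 10 | 24 | 24 − 10 = 14 | +4 | 18 | +4 |

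The discharge version shows the benefit only when the saved ICU days are spent on the ward.

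**Step 3: where the ICU count starts.** Table 3 takes ICU stay from the Other Clinical Event form and does not say that the count begins at first dose. If it includes 2 earlier days, the Step 1 patients have I = 10 and score 10 − 10 = 0 and 20 − 10 = 10. With 3 earlier days, 10 − 11 = −1 is set to 0 and 20 − 11 = 9. The levels shift and the floor can narrow the gap (from 10 to 9 here), but the direction stays.

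**Step 4: in-hospital deaths, discharge version.** Take 20 ICU days by Day 28, so the Day 28 score of a patient alive then is 28 − 20 = 8.

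| Death | Discharge date | Line that applies | Score |
|---|---|---|---|
| Day 27 | none | death prior to Day 28 | 0 |
| Day 28 | none | neither line | missing |
| Day 29 | none | death after Day 28, carries Day 28 score | 8 |
| Day 29 | day 29 | death on recorded discharge date | 0 |

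The last row is not far-fetched: the row for patients discharged alive foresees "Discharge date=Death date (assumptions: patient died in the hospital"). The score of 8 exceeds the 2 given to the Step 1 survivor home on day 10.

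**Step 5: death after discharge, Day 28 version.** Take 8 ICU days, discharge on day 15 and death on day 20. The carried discharge score is 15 − 8 = 7. Read as a cascade, the rule gives 7. If the next line governs, it gives 0. Ventilator-free days and hospital-free days give this patient 0.

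**The case against.** **Reach.** This is one of a long list of secondary endpoints, descriptive and without multiplicity correction, and the Day 28 version is reported beside it. The missing-date lines apply only when both the End of Study date and the fallback Hospital Discharge visit date are absent, and the gap at Day 28 is a single calendar day. All of this stands.

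**The cascade reading.** A reader might infer that the Day 28 rule gives two scores to the same death. The documents do not establish that. The specific exception comes first, and it would never apply if the later line overrode it, so a cascade is the natural reading. Two things remain: the order is left open because the next line lacks an 'Else', and the cascade itself leaves a positive score for a death by Day 28. That may be deliberate credit for leaving hospital alive; the discharged-alive endpoint also disregards later deaths. But that endpoint asks only whether the patient was discharged, whereas the two comparable free-days endpoints give 0, and the value carried over here is the discharge score questioned above.

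**SAP 4.11.** A reader might infer that the SAP contradicts itself by dropping hospital-free days at discharge and keeping ICU-free days at discharge. It does not. The stated reason is "since at discharge the number of hospital-free days will be 0 by definition", and ICU-free days at discharge do vary between patients. The case for change rests on the direction of the score.

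**Whether a test is planned.** SAP 7.2.1 limits tests of continuous variables to change from baseline, which ICU-free days do not have. The endpoint's own section nevertheless specifies the comparison, and summaries by arm would mislead even without a test.

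**Conclusion.** The point holds. At a fixed ICU stay, the discharge version falls by exactly one point per day of earlier discharge until it reaches 0. This follows from the formula and does not depend on the example patients. The exact scores of 2, 12 and 20 do depend on counting ICU stay from first dose, which the documents do not state.

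The death rules are defective as written: 0, missing and 8 for deaths on three successive days with no discharge date, 0 instead of 8 when the discharge date equals the death date, and a positive Day 28 score for some deaths before Day 28. The documents do not show how many of the roughly 66 patients would be affected. The consequence is confined to ICU-free days; the Day 28 score for patients alive at Day 28 is sound, and neither primary endpoint is touched.

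**What to change.** 1. Drop the between-arm comparison of ICU-free days at hospital discharge in SAP 7.2.1.9 and rely on the Day 28 version. Record this in SAP 4.11, because the discharge version is named in the protocol.
2. In the Day 28 version, give 0 to every death on or before Day 28, as for ventilator-free days and hospital-free days, and delete the line that carries over the discharge score.
3. If the discharge version is kept as a description, label it as non-ICU hospital days up to discharge and score every in-hospital death, including those on and after Day 28, by one rule. The tracheostomy and LTAC rows of Table 3 already substitute the death date for a missing discharge date. Doing the same here would remove the dependence on form completion and close the Day 28 gap.
4. State whether recorded ICU stay is counted from first dose.

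The cost is SAP wording, derivation code and one SAP 4.11 entry. No new data are needed.
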